d All subjects who permanently discontinue treatment (discontinuation is considered completion of all treatment) for any reason will undergo a follow-up safety assessment 30 days \pm 3 days after the last dose of treatment. After the safety follow-up visit, subjects who have not progressed will be followed up every 12 weeks as defined in the study. Subjects who undergo surgery for metastases should follow the controls every 12 weeks as established in the protocol. In case of progression by RECIST 1.1 criteria ., Subjects will be monitored for disease status, subsequent cancer treatment, and survival (long-term follow-up).

e All subjects who discontinue treatment prior to disease progression (eg, due to unacceptable toxicities) will be followed up for PFS (eg, radiographic tumor assessments) every 12 weeks until the progression of the disease or the end of the study (unless the reason for abandoning the study was the total withdrawal of consent).

f The end of treatment is understood to be the last day the patient has received the last drug of the combination under test (FOLFOX6 (m) / FOLFIRI (m) / Cetuximab). The safety visit should be carried out 30 \pm 3 days after the end of the treatment, regardless of the cause that caused it. If the patient has not progressed, imaging and biomarker determinations should continue every 12 weeks until progression as specified in this protocol.

g. In order to mobilize any biological sample, the signing of the informed consent will be mandatory. If the patient already has a previous determination of the status of the KRAS gene, he can be included in the test without it being necessary to re-determine the mutational status of K-RAS.

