10.2.2 Secondary endpoints

Objective response rate (ORR): incidence of a CR or PR according to the revised RECIST 1.1 criteria.

Duration of response (RD): (calculated only for subjects having an objective response) time from first objective response to progression of radiological disease according to the revised RECIST 1.1 criteria. For subjects who present a response and have not had progression, the duration of the response will be censored on the last assessment date of the evaluable disease.

Overall survival (OS): Time elapsed from the date of inclusion to the date of death. For subjects who have not died or who have been lost to follow-up by the data analysis cut-off date, the SG will be censored on the date of the last contact.

Safety: Type, frequency, intensity of adverse events related to the combination treatment.

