- h. If thoracic CT scan at selection did not show any chest abnormality, chest X-ray imaging were performed in subsequent evaluations. A CT scan was performed to confirm any abnormality identified upon chest X-ray imaging performed after selection, and all subsequent evaluations were thoracic CT imaging.
- i. Response evaluation was conducted according to the revised RECIST 1.1 criteria, every 12±1 weeks until PD. Subject follow-up was performed regardless of discontinuation or a delay in treatment.
- j. ECOG PS evaluation (on day 1 of each treatment cycle).
- k. Tumour evaluation and serum CEA test was performed every 12 weeks and at the follow-up visit only in subjects who have withdrawn from the trial for reasons different from PD, and in those who have not had a serum CEA test in the previous 12 weeks.
- l. Paraffin embedded tumour block was sent to the central laboratory (Fundación Jiménez Díaz) at selection. The centralised evaluation laboratory perform a tumour block quality assessment. It was compulsory that KRAS and NRAS mutational status (wtKRAS and NRAS) was confirmed by a validated laboratory before the inclusion of any subject.
- m. Follow-up of all subjects who permanently discontinued the treatment before disease progression (e.g. due to unacceptable toxicities) was conducted to evaluate PFS (i.e., tumour imaging) every 12± 1 week until PD or until the end of study (unless the reason for study discontinuation was total consent withdrawal). After PD, all subjects underwent a follow-up assessment of disease status, subsequent cancer therapy, and survival assessment every 12 ± 1 weeks until the end of study (maximum of 24 months).
- n. Blood samples for biomarker analysis were withdrawn before the study treatment initiation and every 12 weeks ± 1 weeks until PD.

Table 3: SDV schedule

Form	Variables
Eligibility	Pathology report, staging, prior treatment.
Demographics	Date of birth, ECOG PS, ICF (signature, date, and completion)
Primary tumour	Diagnosis date, location, staging and surgery
Adjuvant or neoadjuvant treatment	Yes/No
KRAS/NRAS	Central reviewing
Baseline biochemistry and SAE biochemistry	LDH, creatinine, bilirubin, and CEA
Baseline haematology and SAE haematology	Haemoglobin, platelets, and leukocytes

Metastasis	Nº affected organs and hepatic M1 (number and size)
CT scans or MRI	All variables (date, lesions measure, location, new lesions) and RECIST criteria
AEs	Grade and need of SAE communication

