6.5 STATISTICAL METHODS PLANNED IN THE PROTOCOL & DETERMINATION OF SAMPLE SIZE

6.5.1 STATISTICAL AND ANALYTICAL PLANS

6.5.1.1. Primary endpoint

To quantify if the biomarkers BRAF, IGF-1RP/MMP-7 (DP), DP and PIK3CA-PTEN improve the prediction of 12-months progression-free survival (PFS) over the use of just clinical variables in the study population we compared the area under the curve (AUC) of a ROC curve using scores composed by clinical variables with the AUC of scores with the clinical variables plus each of the biomarkers.

PFS was defined as the time from the signature of the ICF date to the radiological progression date or death (whatever occurs first). Subjects who had not shown PD and had not died at database closing were censored on the last date of radiological assessment. Subjects who had concluded study treatment before 48 weeks, due to any cause, underwent follow-up every 12 weeks as described in the protocol. Subjects who had undergone metastatic surgery were not censored on the surgery date but were followed up every 12 weeks until progression was documented. Subjects who received other treatment schemas maintaining the same strategy (chemotherapy + monoclonal antibody) without documented PD, were not censored at the time of the change of treatment. Progression to first line for these patients was considered when applicable according RECIST, independently of treatment received. If by any cause, the baseline CT scan was the only imaging evaluation performed (e.g., subject refusal to stay in the study or lost to follow-up), the case was censored on the inclusion date +1 day.

Two groups with a higher and lower likelihood for tumor progression until 12 months were determined based on the designated classification of clinical variables and following proposed biomarker categories :

1. wt-BRAF vs mutant BRAF

2. wtPI3K and PTEN >3 vs mutant PI3K or PTEN ≤3
3. Non-DP vs DP

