6.5.1.2. Secondary endpoints

- Serum and tumor tissue secondary biomarkers evaluated to predict acquired chemo-resistance including BRAF and PI3K.
- ORR was defined as the incidence of a complete or partial response according to the revised RECIST 1.1 criteria.
- DoR (calculated only for the subjects who present an Overall Response): Time from the first assessment of Overall Response to radiologically-confirmed PD according to the revised RECIST 1.1 criteria. For subjects who showed response and did not show progression, DoR was censored on the last date of assessable disease evaluation reported in the eCRF of the study.
- OS: Time from the signature of the ICF date to date of death. For subjects who did not die or were lost to follow-up on the closing date for data analysis, OS was censored on the date of last contact.
- Safety: Type, frequency, and intensity of AEs related to the combination treatment.

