7. RESULTS

Table 4 Disposition of patients

Patients enrolled	
Received at least one cycle of study treatment	
Evaluable patients	
End of study (evaluable population)	
Death	
Lost to follow-up	
Censored at database closure	
Study completion (24 months of follow-up after PD)	

Table 5 Protocol deviations

Deviation type	Total
Informed consent form	
Efficacy criteria	
Eligibility criteria	
Incorrect dosing regimen	
Other	
Safety	

Table 6. Baseline characteristics by biomarker

	wtBRAF (n=161)	Mutant BRAF (n=20)	p-value*	wtPI3K and PTEN >3 (n=69)	Mutant PI3K or PTEN ≤3 (n=98)	p value*	Non-DP (n=158)	DP (n=23)	p value*
Female									
Mean age (SD)									
Primary location									
Ascending colon									
Transverse colon									
Descending colon									
Sigmoid colon									
Rectum									
Stage									
I									
II									
III									
IV									
Surgery of the primary tumour									
Performance status									
0									
1									
2									
Number of metastatic organs									
0									
1									
2									
3									
4+									
Liver metastasis									
0									
≤3, ≤5 cm									
>3 or >5 cm									
Node metastases¹									
Lung metastases¹									
Peritoneal metastases¹									

Patients with only resectable liver metastases ²									
Chemotherapy									
FOLFOX+Cetuximab									
FOLFIRI+Cetuximab									
Mean Leucocytes (SD)									
Mean Haemoglobin (SD)									
Mean Platelets (SD)									
Mean ALP (SD)									
LDH >450									
Mean CEA (SD)									

¹

- Fisher's exact test for categorical variables and Wilcoxon rank-sum test for ordinal or continuous data

² Missing in one patient The patient does not have metastasis in any other location, and those in the liver are ≤ 3 in number and ≤ 5 cm in size.

Table 7. MEASUREMENTS OF TREATMENT COMPLIANCE

	Total (n=)
Treatment disposition	
Received at least one injection (safety population)	
Efficacy population	
Received at least 12 cycles of cetuximab	
Received at least 12 cycles of chemotherapy+cetuximab	
Received less than 12 cycles of cetuximab	
Received 3 or less administrations of combination	
FOLFOX+cetuximab	
FOLFIRI+cetuximab	
End of Treatment (EOT)	
Reasons for end of treatment	
PD	
PI decision (24 due to surgery, 2 radiotherapy, 2 complete response, 49 others)	

Patient decision	
Toxicity (related to treatment)	
AE (unrelated to treatment)	
No data of EOT available	

Table 8: Patients excluded from the efficacy or safety analysis

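### Objective response has no cut-off at resection, ablation or new anticancer therapy, so surgery can turn stable disease into a counted response

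*SAP*

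**What the plan says.** SAP 6.5.1.2 defines response without a time window: "ORR was defined as the incidence of a complete or partial response according to the revised RECIST 1.1 criteria". Protocol 10.2.2 does the same. The only evaluability rule specific to ORR, in SAP 6.5.1.5, is that a second CT scan must exist.

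The schedule is open-ended. SAP section 6, Table 2, footnote i sets RECIST evaluation every 12±1 weeks until progression and adds: "Subject follow-up was performed regardless of discontinuation or a delay in treatment". SAP 6.5.1.4 has the investigator assess response from the imaging gathered over the whole study, and drops only findings that the investigator calls non-assessable.

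Operated patients stay in the scan programme. Protocol 5.1, note d: "Subjects who undergo surgery for metastases should follow the controls every 12 weeks as established in the protocol". For PFS, SAP 6.5.1.1 makes an explicit choice: "Subjects who had undergone metastatic surgery were not censored on the surgery date but were followed up every 12 weeks until progression was documented".

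Duration of response runs in the protocol as "time from first objective response to progression of radiological disease according to the revised RECIST 1.1 criteria" and in the SAP as "Time from the first assessment of Overall Response to radiologically-confirmed PD according to the revised RECIST 1.1 criteria". For responders without progression, "DoR was censored on the last date of assessable disease evaluation reported in the eCRF of the study". Neither document gives a surgery rule for ORR or for duration of response.

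Surgery was not rare. The Table 7 shell carries the entry "PI decision (24 due to surgery, 2 radiotherapy, 2 complete response, 49 others".

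**The concern.** The secondary objectives (Protocol 4.6.2, SAP 5.2) concern response in patients treated with biweekly cetuximab plus chemotherapy, by biomarker. Removal of a lesion by a surgeon is not a response to that regimen. The PFS rule on surgery is a stated decision and is not questioned here. For ORR no decision is stated, and the open definition combined with the open schedule lets post-operative scans count.

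Three things are at stake:
- The overall ORR and complete response rate, which the SAP also uses to describe the regimen.
- The comparison by BRAF status in Table 9, if conversions are unevenly spread.
- The covariate analysis in SAP 6.5.1.4, which lists resectable liver-only metastases among the groups used to analyse ORR. If post-resection scans count, an association between resectability and ORR would be partly built in.

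**Working it through.** The plan gives no figure to reproduce on this point. The check follows the rules through example records and then bounds the effect with simple proportions.

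**The rules applied to three illustrative records**
1. Stable disease at week 12, target lesions resected at week 18, clean scan at week 24. Progression has not occurred, so week 24 is a scheduled response evaluation. No rule excludes it. If it is read as complete response, the patient enters the ORR numerator.
2. Partial response, then resection, then a clean scan. ORR does not change, but the complete response rate rises by one patient.
3. A responder resected at month 6 who relapses at month 20. The 20 − 6 = 14 post-operative months are included in duration of response.

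**Inputs for size**
- 24 treatment endings for surgery (SAP Table 7; type of surgery and denominator not given).
- 181 patients in the efficacy analysis (SAP synopsis, statistical methods).
- 221 recruited (SAP 6.5.2).
- 161 BRAF wild-type and 20 BRAF mutant (SAP Table 6).
- s = share of the 24 who were stable before surgery and read as responders afterwards. The documents do not give it, so a range is assumed.

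**Upper limit:** 24/181 = 13.3% of the efficacy set (24/221 = 10.9% of those recruited).

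**Rise in ORR = 24 × s / N**

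| s (assumed) | Patients | N = 181 | N = 221 |
|---|---|---|---|
| 10% | 2.4 | 1.3 points | 1.1 points |
| 20% | 4.8 | 2.7 points | 2.2 points |
| 40% | 9.6 | 5.3 points | 4.3 points |
| 50% | 12.0 | 6.6 points | 5.4 points |

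For scale, the 95% half-width of an ORR near 60% (also assumed) is 1.96 × √(0.6 × 0.4/181) = 7.1 points.

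**BRAF contrast**
- Wild-type patients are 161/181 = 89% of the set. With equal resection rates, 24 × 161/181 = 21.3 of the 24 would be wild-type and 2.7 mutant. If conversions follow the same proportion, both groups rise by the same number of points and the contrast does not move.
- If every conversion were wild-type (assumption), that group would rise by 4.8/161 = 3.0 to 9.6/161 = 6.0 points and the mutant group by none.
- One converted patient in the mutant group moves it by 1/20 = 5.0 points.

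The effect on duration of response cannot be computed, because the documents give no operation or relapse times.

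**The case against.** The strongest reply is that no sentence says post-resection scans count towards ORR. The documents give a different purpose for scans after early discontinuation: SAP Table 2, footnote m, and Protocol 5.1, note e, say these patients are followed for PFS. Appendix E, which holds the RECIST version used, is not in the text available here and may address resected lesions. Investigators may also call a post-operative scan non-assessable.

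Part of this stands. The conclusion is about what the rules permit, and it assumes that Appendix E contains no surgery rule. But stating that scans serve PFS does not remove them from a response definition without a cut-off, when footnote i keeps response evaluation going until progression. The non-assessable exclusion is left to site judgement and is not tied to surgery, so two sites could score the same patient differently.

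The objection on duration of response also stands. Leaving it uncensored at surgery matches the deliberate PFS rule, and censoring at resection could be informative if the patients resected are those with the better outlook. A reader might infer that duration of response must be censored at surgery; the documents do not support that as the only sound choice.

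A reader might also infer that, if most resected patients are BRAF wild-type, the BRAF comparison is biased. It is not on that ground alone: with 161 of 181 wild-type, most resected patients would be wild-type under equal resection rates.

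**Conclusion.** The point holds as a gap that should be closed. The written rules allow a patient with stable disease to become a counted responder because the target lesions were removed, so ORR and the complete response rate can be inflated. Under the assumed 20–40% share, the rise in ORR is 2.7–5.3 points on 181 patients, somewhat smaller than the sampling half-width of about 7 points but all in one direction.

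It would go too far to say that the reported rates are inflated, or that 13.3 points of response are surgical. The documents give no responses before and after surgery. The 13.3% figure would require all 24 operations to involve target lesions, all 24 patients to be in the efficacy set, and every one to be newly read as a responder. Equally, the 24 may miss patients operated on after treatment ended for another reason.

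The Table 9 contrast covers BRAF only and does not include duration of response. It is affected only if conversions are out of proportion to 161:20. ORR and duration of response are secondary endpoints, and the primary 12-month PFS/AUC comparison does not depend on this rule.

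**What to change.** In SAP 6.5.1.2 and 6.5.1.5:
- Derive best overall response only from scans up to the earliest of progression, resection or ablation of target lesions, or start of another anticancer therapy.
- Report the present all-scans rule as a sensitivity analysis.
- Report, by biomarker group, the number of resections and the number of responses first recorded after surgery.
- Keep the current definition of duration of response, in line with the PFS rule on surgery, say so explicitly, and add a sensitivity analysis censored at the last scan before surgery or new therapy.

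The cost is SAP wording and a re-derivation. Scan dates, lesion measurements, treatment end dates and reasons for ending are among the source-verified items in SAP Table 3. Dates of metastasis surgery, ablation and new therapy are not listed there and may need to be confirmed in the database. The stated ORR and complete response rate may be slightly lower.

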6.5.1.3. Analysis population

Efficacy variables were analysed in all subjects who provided their informed consents, were included in the trial and did not present significant protocol deviations throughout the study period.

An intention-to-treat analysis in all patient enrolled into the study was not performed because the primary study objective was to evaluate the predictive value of the three biomarker BRAF, IGF-1RP/MMP-7 (Double-positive Phenotype/DP) and PI3K-PTEN on PFS in wt-RAS CRC patients receiving standard chemotherapy plus bi-weekly cetuximab as first-line therapy, but patients with significant protocol deviations (e.g. RAS mutations, missing biomarker data and those not receiving cetuximab treatment) could not contribute to the investigation of the primary objective.

All patients who received study medication were included in the safety analysis. .

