10. STATISTICAL CONSIDERATIONS

10.1 Study design

Prospective, multicenter, phase II clinical trial designed for the evaluation of predictive tumor biomarkers in patients with advanced and / or metastatic colorectal cancer and non-mutated KRAS tumor treated with biweekly cetuximab as first-line treatment.

The main objective of this study is the validation of the biomarkers BRAF, IGF1P / MMp7 (DP) and PI3K-PTEN to predict PFS in patients with advanced and / or metastatic colorectal cancer with non-mutated KRAS treated with standard chemotherapy plus biweekly cetuximab as first line therapy.

The primary endpoint and secondary efficacy endpoint analysis will be based on the revised RECIST 1.1 criteria (Appendix E) for the intention-to-treat analysis group.

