10.2.3 Subgroup analysis

The intention-to-treat (ITT) analysis group is defined as all subjects who signed the informed consent and who have received the trial treatment, regardless of whether they actually receive any dose of the study treatment. Efficacy presentations will be made to the ITT review group.

A secondary analysis group (analysis group per protocol) will be used to evaluate the efficacy variables in all subjects who signed the informed consent and were included in the study and who did not present significant deviations from the protocol.

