10.3 General considerations

The primary endpoint and secondary efficacy endpoints will be analyzed using the ITT analysis group and the per-protocol analysis group.

Efficacy analyzes will be based on radiographic images collected during the study and analyzed by the investigator. Any examination that the investigator classifies as not evaluable will be omitted from the analysis (it will be considered as no examination).

For continuous variables, the mean, standard error (for efficacy variables) or standard deviation (for other measurements), median, 25th percentile, 75th percentile, minimum, and maximum will be provided. For discontinuous data, the frequency and percentage distributions will be provided. The two-sided 95% confidence intervals of the Kaplan-Meier quartiles will be calculated using the methods described by Brookmeyer and Crowley (Brookmeyer, 1982). Two-sided 95% confidence intervals for the Kaplan-Meier rates at specific time points will be calculated using the methods described by Collett (Collett, 1992).

Safety data will be analyzed throughout the study.

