Statistical methods	
Sample size considerations
 
Initially, the number of patients required to be recruited in 24 months was 155 and the total study duration (recruitment + follow-up) was considered to be 28 months for 115 events to occur. After recruiting 157 patients, it was determined that about 70 of these patients had insufficient samples for biomarker analysis preventing their inclusion in the analysis of the primary objective. Therefore, in order to reach the 115 events necessary to evaluate the primary endpoint, the total number of patients to be included in the trial was increased up to 240. Finally, 221 patients were considered sufficient to observe the required number of events. After central reviewing and monitoring, 181 patients with wt-RAS were finally included for efficacy analysis.
 
For sample size calculation, it was assumed that patients could be classified into 2 groups based on their clinical characteristics and their biomarker profile. The log-rank method was planned to be used for the comparison of PFS during follow-up between the two groups. A minimum difference in PFS of 20% (50% vs 30%) was expected between the groups at 12 months, given the following assumptions:
 
 • Alpha error (two-tailed): 5% • Beta error: 20% 
Statistical considerations
 
The primary and the secondary efficacy objectives were analysed using per-protocol analysis. Patients fulfilling all eligibility criteria and with documented wt-RAS status (KRAS and NRAS) were included in the efficacy analysis.
 
Efficacy analysis was based on radiological imaging performed throughout the study and assessed by site investigators. Any finding considered as non-evaluable by the investigator was excluded from the analysis (it was considered as non-existent).
 
For continuous variables, mean, standard error (for efficacy variables), standard deviation (for other measurements), median, 25th percentile, 75th percentile, minimum and maximum, were considered. Categorical variables are presented using frequencies and percentages.
 
The 95% two-sided confidence intervals (CI 95%) of Kaplan–Meier

---------------------	---

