6.5.1.5. Analysis of main study variables

The primary efficacy analysis of this trial was performed based on all subjects who provided their informed consents, were included in the trial, and did not present significant protocol deviations throughout the study period. .

Continuous and ordinal variables between independent groups were compared using the Wilcoxon rank-sum test and proportions were compared with Fisher's exact test. Clinical endpoints were ORR, DoR, PFS, and OS. Tumour assessments by CT scans were performed every 3 months until PD. Patients without a second CT scan evaluation were not assessable for ORR.

PFS was defined as the time of the signature of the ICF date until PD or death from any cause. Patients who did not experience PD or death were censored on the date of last examination. For more information regarding censoring see in Section 7.5.1.1. OS was defined as the time from the signature of the ICF date to death from any cause. Patients lost to follow-up or still in the study at database closure have been censored at the date last known to be alive.

Survival analyses including PFS and OS were performed using Kaplan–Meier methods. Cox proportional hazards regression with the Efron method for ties was used to identify prognostic factors for PFS and OS.

Multivariable analysis was performed using subject-matter knowledge and deciding a *priori* the variables to adjust by age (>65 years), sex, tumour site (right vs left), surgery of primary tumour, liver only metastases (<3 nodules and <5 cm vs >3 nodules or >5 cm), ECOG PS, LDH (>450 U/L) and CEA, BRAF mutational status, and type of therapy. This analysis was later adjusted by variables with p-values <0.10 in the

univariate analysis via the automated stepwise selection of variables (p-value for variable entry into the model was 0.2 and p-value to keep the variable in the model was 0.1).. All p-values were two sided.

The proposed sample size ensures establishing a consistent multivariable analysis. Clinical variables and biomarkers were used to build scores intended to predict 12- months PFS as following:

1. A multivariable Cox model was built with those clinical variables that in the univariate analysis had a p-value ≤ 0.15 (PS, chemo regimen, sidedness, resectable liver metastases).

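### The SAP drops the protocol's ITT efficacy analysis for a set open to exclusion after consent, with no closed deviation list and no wider-set check

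*SAP*

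**What the plan says.** **Protocol.** Section 10.1: "The primary endpoint and secondary efficacy endpoint analysis will be based on the revised RECIST 1.1 criteria (Appendix E) for the intention-to-treat analysis group". Section 10.2.3 defines the ITT group and then adds: "A secondary analysis group (analysis group per protocol) will be used to evaluate the efficacy variables". Section 10.3 commits to both: "The primary endpoint and secondary efficacy endpoints will be analyzed using the ITT analysis group and the per-protocol analysis group".

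**SAP.** Section 6.5.1.3 limits efficacy to consented, included subjects who "did not present significant protocol deviations throughout the study period". It then states: "An intention-to-treat analysis in all patient enrolled into the study was not performed". The reason given is that "patients with significant protocol deviations (e.g. RAS mutations, missing biomarker data and those not receiving cetuximab treatment") could not inform the primary objective. Section 6.5.1.5 applies the same restriction to the main analysis: "The primary efficacy analysis of this trial was performed based on all subjects who provided their informed consents", followed by the same deviation condition.

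The SAP synopsis (Statistical considerations) calls the analysis per-protocol but words membership differently: "Patients fulfilling all eligibility criteria and with documented wt-RAS status (KRAS and NRAS) were included in the efficacy analysis".

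PFS runs from signature of the consent form (6.5.1.1). Table 5 lists deviation types, among them dosing errors and catch-all rows, without marking which of them remove a patient. Table 8 is a shell for a patient-level listing of reasons for exclusion. Only the safety analysis uses all treated patients.

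**The concern.** An efficacy set that depends on conduct during the whole study can select on what happens after time zero. Dosing deviations, early stopping and similar events may be related to toxicity or prognosis, so removing those patients can change the relation between a marker and 12-month PFS. The protocol guarded against this by placing per-protocol beside ITT. The SAP keeps only the restricted set and plans nothing against which to check it.

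The set also cannot be rebuilt from the text: the examples are not a definition, and the synopsis and section 6.5.1.3 do not state the same rule. The result that depends on it is a ranking of four scores whose AUCs differ by 0.02 or less from the clinical score, and that ranking is used to name the most suitable score (6.5.1.5, step 7).

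**Working it through.** **1. The membership rules side by side.**

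| Place | Efficacy set | Can a later deviation remove a patient? |
|---|---|---|
| Protocol 10.1, 10.2.3, 10.3 | ITT, with per-protocol as secondary | ITT: no. Per-protocol: yes |
| SAP synopsis | All eligibility criteria met and wild-type RAS documented | No, as worded |
| SAP 6.5.1.3 and 6.5.1.5 | Consented, included, no significant deviation during the study | Yes, as worded |

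**2. Does the SAP's reason cover its rule?** It names three grounds. RAS mutation and missing tumour markers are baseline facts. Not receiving cetuximab is settled after consent but is tied to the objective. None of the three reaches a treated, wild-type RAS patient with a known marker who deviates later, yet the wording allows that patient to be removed.

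**3. Counts.**
- Table 6, BRAF: 161 + 20 = 181. Double-positive (DP): 158 + 23 = 181. Both reproduce the synopsis figure of 181.
- Outside the set: 221 − 181 = 40, and 40/221 = 18.1%. The planned non-evaluable share was 10% (protocol 10.2.5, SAP 6.5.2).
- Table 6, PI3K-PTEN: 69 + 98 = 167, and 181 − 167 = 14 (14/181 = 7.7%). These 14 have no PI3K-PTEN group but remain in the 181, so missing marker data was not a ground for leaving the whole set in every case.

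**4. The reported quantity** (SAP synopsis, risk model). AUC with each marker minus the clinical AUC:
- BRAF: 0.68 − 0.67 = +0.01 (p = 0.37)
- PI3K-PTEN: 0.69 − 0.67 = +0.02 (p = 0.32)
- DP: 0.66 − 0.67 = −0.01 (p = 0.09)

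**5. A hypothetical shift.** A simulation used the synopsis coefficients (0.6, −0.5, −0.4) scaled by 1.15, which puts the clinical AUC at about 0.66 to 0.69. Its assumptions, which are not in the documents, are factor prevalences of 50%, 75% and 10%, exponential PFS with 30% to 50% progression-free at 12 months, and a true marker hazard ratio of 1 or 1.79. The marker coefficient in the score was set at log(1.79), borrowed from the planning hazard ratio in SAP 6.5.2.
- Restoring 3 BRAF-mutant patients moves the BRAF increment by +0.005 to +0.008 if all three had progressed by 12 months, and by −0.009 to −0.016 if none had.
- Three mutants is a demanding case. The mutant share is 20/181 = 11.05%, so 3 correspond to 3/0.1105 ≈ 27 excluded patients of this kind. With 10 such patients, the binomial chance of 3 or more mutants is about 9%.

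**6. Were the AUCs compared in the same patients?** From the confidence intervals, SE = (0.75 − 0.60)/3.92 = 0.0383 for the clinical score and (0.76 − 0.61)/3.92 = 0.0383 for PI3K-PTEN. If the two were independent, the SE of the difference would be 0.0383 × √2 = 0.054, z = 0.02/0.054 = 0.37 and p ≈ 0.71. The SAP reports 0.32. The same step gives about 0.85 for BRAF (reported 0.37) and 0.85 for DP (reported 0.09). The reported p-values therefore look like paired tests. What remains open is whether the displayed 0.67 rests on 181 patients while the 0.69 rests on 167.

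**The case against.** The strongest reply is that the phrase about the study period is being made to carry too much. The synopsis ties the 181 to central review, monitoring and wild-type RAS status. Section 6.5.1.1 keeps patients after post-baseline events: those with only a baseline CT are censored one day after inclusion, and those who have metastatic surgery stay in follow-up. Table 7 tabulates short exposure and does not make it a ground for exclusion. Table 8 already plans to list reasons, and it is empty because it is a shell. The trial is single-arm, so ITT protects no randomised comparison. The protocol's ITT sentence contradicts itself by requiring treatment and then disregarding whether any dose was given, and its own per-protocol set used the same undefined term.

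Much of this stands. It makes baseline reasons likely for many of the 40, and it shows that a literal all-enrolled ITT is not the right remedy for this objective. It does not remove the mismatch between the two SAP rules, close the list of deviations or supply the missing check. In the protocol the vague per-protocol set was secondary and stood beside ITT; in the SAP it stands alone.

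A reader might infer that patients were in fact removed for post-baseline deviations. The documents do not show this. A reader might also infer that the clinical and PI3K-PTEN scores were tested in different patients; the reported p-values point the other way.

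**Conclusion.** The point holds as a defect of definition and of a missing check, and it should be corrected. The departure from the protocol, the open-ended rule and the conflict with the synopsis can be read directly from the text, and confidence in them is high.

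The effect on the result cannot be sized. Forty of 221 patients (18.1%) are outside the set, the split by reason is not given, and neither the direction nor the amount of any bias is known. The simulated AUC shifts are hypothetical: they need several excluded patients with the same marker status and the same outcome, and they show only that the reported increments are small enough to be sensitive.

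A reader might infer that a wider set would overturn the marker conclusion. The documents do not support that. The SAP already describes all four scores as having similarly low discrimination, and no comparison has a p-value below 0.09.

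**What to change.** - **One primary efficacy set**, worded identically in the synopsis, 6.5.1.3 and 6.5.1.5 and defined by baseline facts: enrolled, wild-type RAS confirmed and the relevant marker measured, regardless of later deviations.
- **If starting study treatment stays a condition**, because the objective concerns cetuximab-treated patients, state that it falls after consent and include never-starters in a sensitivity analysis.
- **Per-protocol as a sensitivity analysis**, with a closed list of significant deviations mapped to the Table 5 types.
- **Table 8**: mark each reason for exclusion as baseline or post-baseline.
- **Reporting clarification**: give the clinical-score AUC in the same patients as each marker score, with n (currently 181 for BRAF, 167 for PI3K-PTEN and 181 for DP).

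The cost is SAP wording and a re-run on data already collected. No sample-size figure changes. Estimates may move slightly in either direction.
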